SYNOPSIS

Protocol Title:	A Multi-Center, Double-Masked, Randomized, Vehicle- and Active-Controlled, Phase 3 Study Evaluating the Efficacy and Safety of Bilastine Ophthalmic Solution 0.6% Compared to Vehicle and Zaditen (Ketotifen Ophthalmic Solution 0.025%) for the Treatment of Allergic Conjunctivitis in the Conjunctival Allergen Challenge (Ora-CAC®) Model
Protocol Number:	17-100-0012/BOFT-0218/AC-CAC
Investigational Product:	Bilastine Ophthalmic Solution 0.6%
Study Phase:	Phase 3
Primary Objective:	To evaluate the efficacy of Bilastine ophthalmic solution 0.6% compared to vehicle and Zaditen (Ketotifen ophthalmic solution 0.025%) for the treatment of the signs and symptoms of allergic conjunctivitis.
Secondary Objectives:	To evaluate the safety and tolerability of Bilastine ophthalmic solution 0.6% compared to vehicle and Zaditen (Ketotifen ophthalmic solution 0.025%)
Overall Study Design:	
Structure:	
Screening Period: At Visit 1, subjects will sign the informed consent and an allergic skin test will be performed, if required. At Visit 2, each qualifying subject will undergo a bilateral conjunctival allergen challenge (CAC) titration using an allergen they had a positive reaction to on their skin test. Subjects who elicit a positive reaction post-CAC will undergo the confirmation CAC at Visit 3 using the same allergen they qualified with at Visit 2.
 
Treatment Period: Treatment will begin at Visit 4a after subjects are randomized. At this visit, subjects will receive an in-office dose of the treatment they were randomized to receive. Approximately 16 hours post-instillation of study medication, subjects will undergo CAC at Visit 4b. Subjects will receive a final dose of study medication at Visit 5

	
approximately 15 minutes prior to CAC.
 
Follow-Up Period: A documented telephone call will be made by the investigator (or investigator's designee) on Day 15 (± 3) to all randomized subjects approximately one week after their last visit to query if there have been any changes in their medical history or medications or if they have had any emergency room visits or hospitalizations since their last study visit. Documentation will be made to record this telephone call follow-up.

Duration:	This study consists of six (6) office visits over a period of approximately five to nine (5-9) weeks.
Controls:	
• Vehicle of Bilastine Ophthalmic Solution• Zaditen (Ketotifen ophthalmic solution 0.025%)
Dosage/Instillation:	
At Visit 4a, a trained study technician will instill one (1) drop of assigned investigational product into each eye approximately 16 hours (+1 hour) prior to the Visit 4b CAC using the designated bottle .
 
At Visit 5, a trained study technician will instill one (1) drop of assigned investigational product into each eye approximately 15 minutes (+1 minute) prior to the Visit 5 CAC using the designated bottle 1.
 
The pre-specified technicians responsible for instilling the investigational product will not be involved with any other clinical study procedures at the site.

Summary of Visit Schedule:	
Visit 1 (Day -50 to Day -22): Screening / Informed Consent / Skin Test
 
Visit 2 (Day -21 \pm 3): Titration CAC
 
Visit 3 (Day -14 \pm 3): Confirmation CAC
 
Visit 4a (Day 1): Enrollment / Randomization / In-Office Instillation
 
Visit 4b (16 hours from Visit 4a): 16 Hour

	
Duration of Action CAC
 
Visit 5 (Day 8 ± 3): In-Office Instillation / 15-Minute Onset of Action CAC
 
Day 15 (± 3): Follow-Up Telephone Call

Measures Taken to Reduce Bias:	Randomization will be used to avoid bias in the assignment of subjects to investigational product, to increase the likelihood that known and unknown subject attributes (e.g. demographics and baseline characteristics) are evenly balanced across treatment groups, and to enhance the validity of statistical comparisons across treatment groups. Finally, masked treatment will be used to reduce potential of bias during data collection and evaluation of clinical endpoints.
Study Population Characteristics:	
Number of Subjects:	Approximately 225 subjects will be enrolled at up to seven (7) sites.
Condition/Disease:	Allergic Conjunctivitis
Inclusion Criteria:	
1) be at least 18 years of age at Visit 1 of either gender and any race (a government issued ID will be verified at the time ICF is signed);2) provide written informed consent and sign the HIPAA form;3) be willing and able to follow all instructions and attend all study visits;4) have a positive history of ocular allergies and a positive skin test reaction to a seasonal (grass, ragweed, and/or tree pollen) or perennial allergen (cat dander, dog dander, dust mites, cockroach) as confirmed by an allergic skin test conducted at Visit 1 or within the last 2 months;5) be able and willing to avoid all disallowed medications for the appropriate washout period and during the study (see exclusion 6);6) be able and willing to discontinue wearing contact lenses for at least 72 hours prior to Visit 2 and during the study trial period;7) (for females capable of becoming pregnant) agree to have urine pregnancy testing performed at screening on Visit 2 and Visit 4a (must be

	
negative) and exit visit; must not be lactating; and must agree to use a medically acceptable form of birth control¹ throughout the study duration. Women considered capable of becoming pregnant include all females who have experienced menarche and have not experienced menopause (as defined by amenorrhea for greater than 12 consecutive months) or have not undergone successful surgical sterilization (hysterectomy, bilateral tubal ligation, or bilateral oophorectomy);
 
8) have a calculated visual acuity of [REDACTED] or better in each eye as measured using an ETDRS chart;
 
9) have a positive bilateral post-CAC reaction [REDACTED] [REDACTED] [REDACTED] within 10 (± 2) minutes of instillation of the last titration of allergen at Visit 2;
 
10) have a positive bilateral post-CAC reaction [REDACTED] [REDACTED] for at least two out of the first three time points² following the challenge at Visit 3.

Exclusion Criteria:	
1) have known contraindications or sensitivities to the use of the investigational product or any of its components;
 
2) have any ocular condition that, in the opinion of the investigator, could affect the subject's safety or trial parameters (including but not limited to narrow angle glaucoma, clinically significant blepharitis, follicular conjunctivitis, iritis, pterygium or a diagnosis of dry eye);
 
3) have had ocular surgical intervention within three (3) months prior to Visit 1 or during the study and/or a history of refractive surgery within the past six (6) months;
 
4) have a known history of retinal detachment, diabetic retinopathy, or active retinal disease;

¹Acceptable forms of birth control are spermicide with barrier, oral contraceptive, injectable or implantable method of contraception, transdermal contraceptive, intrauterine device, or surgical sterilization of partner. For non-sexually active females, abstinence will be considered an acceptable form of birth control.

² not necessarily at the same time point

	
5) have the presence of an active ocular infection (bacterial, viral or fungal) or positive history of an ocular herpetic infection at any visit;
 
6) use any of the following disallowed medications during the period indicated prior to Visit 2 and during the study:
 
7 Days
 
• systemic or ocular H₁ antihistamine, H₁ antihistamine/mast cell stabilizers, H₁ antihistamine- vasoconstrictor drug combinations;• decongestants;• monoamine oxidase inhibitors;• all other topical ophthalmic preparations (including artificial tears);• lid scrubs;• topical prostaglandins or prostaglandin derivatives;• ocular, topical, or systemic nonsteroidal anti-inflammatory drugs (NSAIDs); *Baby aspirin (81 mg) is allowed as long as a stable dose has been maintained for at least 30 days prior to Visit 1 and will continue to be maintained for the duration of the study. 
14 Days
 
• inhaled, ocular, topical, or systemic corticosteroids or mast cell stabilizers; 
45 Days
 
• depo-corticosteroids; 
Note: Currently marketed over-the-counter anti-allergy eye drops (i.e. anti-histamine/ vasoconstrictor combination products such as Visine®-A®) may be administered to subjects by trained study personnel at the end of Visits 2, 3, 4b, and 5, after all evaluations are completed.
 
7) have any significant illness (e.g. any autoimmune disease requiring therapy, severe cardiovascular disease [including arrhythmias] the investigator feels could be expected to interfere with the subject's health or with the study parameters

--	----------------------------------------------------------------------------------------------------------------------------------------------------------------------------------------------------------------------------------------------------------------------------------------------------------------------------------------------------------------------------------------------------------------------------------------------------------------------------------------------------------------------------------------------------------------------------------------------------------------------------------------------------------------------------------------------------------------------------------------------------------------------------------------------------------------------------------------------------------------------------------------------------------------------------------------------------------------------------------------------------------------------------------------------------------------------------------------------------------------------------------------------------------------------------------------------------------------------------------------------------------------------------------------------------------------------------------------------------------------------------------------------------------------------------------------------------------------------------------------------------------------------------------------------------------------------------------------------------------------------------------------------------------------------------------------------------------------------------------------------------------------------------------------------------------------------------------------------------------------------------------------------------------------

	
and/or put the subject at any unnecessary risk (includes but is not limited to: poorly controlled hypertension or poorly controlled diabetes, a history of status asthmaticus, organ transplants, a known history of persistent moderate or severe asthma, or a known history of moderate to severe allergic asthmatic reactions to any of the study allergens;
 
8) have received allergy immunotherapy within the last 2 years;
 
9) manifest signs or symptoms of clinically active allergic conjunctivitis in either eye at the start of Visits 2, 3 or 4 [REDACTED] [REDACTED];
 
10) have a history of glaucoma or ocular hypertension;
 
11) have planned surgery (ocular or systemic) during the trial period or within 30 days after;
 
12) have used an investigational drug or medical device within 30 days of the study or be concurrently enrolled in another investigational product trial;
 
13) be a female who is currently pregnant, planning a pregnancy, or lactating.

Study Formulations and Formulation Numbers:	
• Bilastine Ophthalmic Solution 0.6%• Zaditen (Ketotifen ophthalmic solution 0.025%)• Vehicle of Bilastine Ophthalmic Solution
Evaluation Criteria:	
Efficacy Measures and Endpoints:	
Primary:
 
• Ocular itching evaluated by the subject at 3(± 1), 5(± 1), and 7(± 1) minutes post-CAC [REDACTED] at Visits 4b and 5. 
Secondary:
 
The following assessments will occur at 7(± 1), 15(± 1), and 20(± 1) minutes post-CAC [REDACTED]

	
[REDACTED] at Visits 4b and 5:
 
• Conjunctival redness evaluated by the investigator• Ciliary redness evaluated by the investigator• Episcleral redness evaluated by the investigator• Chemosis evaluated by the investigator• Eyelid swelling evaluated by the subject• Tearing evaluated by the subject• Rhinorrhea, nasal pruritus, ear or palate pruritus, and nasal congestion evaluated by the subject
Safety Measures:	
• Adverse Events assessed at all office visits• Visual Acuity at Distance Utilizing an ETDRS chart conducted at Visit 2, 3, 4a, 4b and 5.• Slit lamp Biomicroscopy conducted at Visit 2, 3, 4a, 4b and 5.• Intraocular Pressure measured at Visit 2 and Visit 5• Dilated Fundoscopy measured at Visit 2 and Visit 5.
Other:	
Tolerability Measures:
 
• Drop comfort assessment (assessed by subjects upon instillation, at 1, and 2 minutes post-instillation) at Visit 4a.• Drop descriptor query (assessed at 3 minutes post-instillation) at Visit 4a.

General Statistical Methods and Types of Analyses
 
Primary Hypothesis:
 
Statistical hypotheses for the ocular itching endpoint are as follows and will be tested in hierarchical order:
 
[REDACTED]
	

Sample Size:

Approximately 225 subjects will be randomized at Visit 4a in a [REDACTED] across the three treatment arms (90 Bilastine; 90 Ketotifen; 45 Vehicle). It is expected that approximately [REDACTED] of subjects will discontinue from the trial prior to completing Visit 5.

Power to Test H_{01}

Power to Test H_{02}

Power to Test H_03

Multiplicity Adjustments:

A hierarchical testing procedure will be used to maintain an overall

Safety Analyses:

The incidence of subjects with any treatment-emergent adverse events (TEAEs) during the study will be the key safety variable. The percentage of subjects with any TEAE will be summarized for each treatment group for ocular and non-ocular TEAEs separately. Incidence will be tabulated by MedDRA system organ class and preferred term within each system organ class. TEAEs will also be summarized for related treatment-emergent adverse events (rTEAEs) and SAEs, and by maximal intensity. All n-TEAEs and TEAEs (hereinafter referred as AEs) will be coded using latest available MedDRA version.

All AEs will be listed by subject. TEAEs listing will include the TEAE, treatment group, onset and stop date, intensity, relationship to study medication, and seriousness. Separate listings will be prepared, if applicable, for subjects who experience a SAE and for subjects who discontinue because of an TEAE.

Other safety variables, including slit lamp biomicroscopy, dilated fundus examination, visual acuity, and IOP, will be summarized descriptively using quantitative and qualitative summary statistics as appropriate. Changes and shifts from baseline will also be summarized where applicable.

Summary of Known and Potential Risks and Benefits to Human Subjects

Bilastine was demonstrated to be safe and efficacious in treating ocular itching associated with allergic conjunctivitis in the Phase 2 topical ocular clinical study. In this study, 19 TEAEs were reported by 18 of the 121 subjects. Seven of these AEs were

reported in the vehicle group. Eight of the 19 TEAEs were ocular TEAEs, and 11 were non-ocular TEAEs. Most (13) subjects who reported TEAEs identified them as mild in severity, while 5 subjects reported TEAEs of moderate severity. The Bilastine 0.6% group had one non-ocular TEAE (hypoesthesia) that was mild in severity and considered not related to treatment; the investigator decided to withdraw treatment for this subject. One subject in the Bilastine 0.4% group had a TEAE (mild headache) that was considered to be related (definite/certain) to treatment. Visual acuity reduced was reported by two subjects in the Bilastine 0.2% group and were not reported in any of the other treatment groups; these TEAEs were mild in severity and were considered not related to treatment.

The most frequently reported ocular TEAE in the Phase 2 study was visual acuity reduced. Other ocular TEAEs reported (one TEAE each) included blepharitis, macular fibrosis, hordeolum, and keratitis in the bilastine groups, and corneal deposits and eye discharge in the vehicle group. The most frequently reported non-ocular TEAE was viral upper respiratory tract infection. Other non-ocular TEAEs reported (one each) included pyrexia, nephrolithiasis, headache, and hypoesthesia in the bilastine groups and gastroenteritis viral and arthralgia in the vehicle group. Subjects assessed tolerability (drop comfort) as comfortable in all treatment groups. Bilastine 0.6% showed strong efficacy for onset of action at 15 minutes and at 16 hours, indicating that it could be used for once daily treatment of allergic conjunctivitis.

Several bilastine clinical studies via oral administration have shown efficacy and safety for the treatment of nasal as well as non-nasal (i.e., ocular) symptoms of rhinoconjunctivitis. The incidence of somnolence and fatigue as adverse events in 10 Phase II and III studies in patients treated with oral bilastine was comparable to placebo and significantly lower than in patients receiving active comparators, including cetirizine. Preclinical studies in several species with oral bilastine and subsequent toxicokinetic (TK) modeling for ocular administration demonstrated that bilastine showed systemic toxicity only at concentrations significantly higher than the proposed topical ocular dosing. Bilastine 20 mg tablets are authorized in the European Economic Area (29 countries) and in over 86 other countries worldwide for the symptomatic treatment of allergic rhinoconjunctivitis and urticaria in adults and adolescents older than 12 years. Post-marketing experience in the EEA and other countries has included cumulative human exposure of approximately 71,769,892 therapeutic cycles or 4,129,226 patient-years to oral bilastine 20 mg tablets, with no new safety findings. The most frequently reported treatment-related TEAEs across 10 Phase II and Phase III bilastine oral administration clinical studies were headache, somnolence, fatigue, dizziness, and upper abdominal pain, with similar percentages of patients reporting related TEAEs in the bilastine and placebo groups. Other possible, uncommon adverse reactions include abnormal ECG and liver changes indicated by blood tests. The safety profile of oral bilastine in adolescent patients, in children from 2 to 11 years, and in elderly patients has been similar to that in adults.

Zaditen has been associated with the following side effects:

After drug instillation, transient blurred vision or somnolence may occur, which can affect driving or the capacity to operate machines.

Immune system disorders

Uncommon: Hypersensitivity

Nervous system disorders

Uncommon: Headache

Eye disorders

Common: Eye irritation, eye pain, punctate keratitis, punctate corneal epithelial erosion.
Uncommon: Vision blurred (during instillation), dry eye, eyelid disorder, conjunctivitis, photophobia, conjunctival haemorrhage.

Gastrointestinal disorders

Uncommon: Dry mouth

Skin and subcutaneous tissue disorders

Uncommon: Rash, eczema, urticaria

General disorders and administration site conditions

Uncommon: Somnolence

Adverse drug reactions from post-marketing experience (Frequency not known):

Hypersensitivity reactions including local allergic reaction (mostly contact dermatitis, eye swelling, eyelid pruritis and oedema), systemic allergic reactions including facial swelling/oedema (in some cases associated with contact dermatitis) and exacerbation of pre-existing allergic conditions such as asthma and eczema.

The use of oral dosage forms of ketotifen may potentiate the effect of CNS depressants, antihistamines and alcohol. Although this has not been observed with Zaditen eye drops, the possibility of such effects cannot be excluded.

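### As worded in the synopsis, exclusion criterion 6 does not bar a plain intranasal H1 antihistamine, although three nasal symptoms are secondary efficacy measures

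*Combined protocol and SAP*

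**What the plan says.** Exclusion criterion 6 covers both the washout and the study itself: subjects may not "use any of the following disallowed medications during the period indicated prior to Visit 2 and during the study". Under its 7-day heading, the antihistamine item opens with "systemic or ocular H₁ antihistamine" and continues with "H₁ antihistamine/mast cell stabilizers, H₁ antihistamine- vasoconstrictor drug combinations". Decongestants follow, with no route stated.

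Other classes have their own route lists. The 7-day list has "ocular, topical, or systemic nonsteroidal anti-inflammatory drugs (NSAIDs", and the 14-day list has "inhaled, ocular, topical, or systemic corticosteroids or mast cell stabilizers". The one catch-all is "all other topical ophthalmic preparations (including artificial tears".

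Under Efficacy Measures and Endpoints, the primary measure is ocular itching at 3, 5 and 7 minutes after challenge at Visits 4b and 5. For the secondary measures the synopsis states: "The following assessments will occur at 7(± 1), 15(± 1), and 20(± 1) minutes post-CAC", at the same two visits. The last secondary bullet contains rhinorrhea, nasal pruritus, ear or palate pruritus and nasal congestion, all rated by the subject.

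**The concern.** Every subject has a confirmed seasonal or perennial allergy, and three of the secondary symptoms are scored in the nose. A site that screens against the criterion as written could accept a subject who uses a plain antihistamine nasal spray, and that subject could go on using it through the treatment visits. If the spray reduces nasal symptoms, that subject's nasal scores after challenge reflect the spray as well as the assigned eye drop. What is at stake is how the nasal secondary comparisons can be interpreted.

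**Working it through.** The plan gives no figure to reproduce, and the main check is of wording.

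**1. Does the antihistamine line reach an intranasal product?** The spray is not ocular. Reading *systemic* broadly enough to include it does not fit the rest of the list. The NSAID line names *topical* as well as *systemic*, and the corticosteroid and mast cell stabilizer line names *inhaled* and *topical* as well. The criterion therefore treats local routes as separate from systemic and names them where it wants them barred. The antihistamine line names only the eye.

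**2. How much is left open?** Oral antihistamines are systemic. Antihistamine/mast cell stabilizer products, antihistamine-vasoconstrictor combinations and decongestants are listed without a clear route limit of their own, so intranasal forms of these are arguably barred. The gap is a plain H1 antihistamine given intranasally.

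**3. Does anything else visible close it?**
- Inclusion criterion 5 only refers back to exclusion criterion 6.
- The catch-all is limited to ophthalmic products.
- Exclusion criterion 9, as far as it is visible, concerns the eye: "manifest signs or symptoms of clinically active allergic conjunctivitis in either eye at the start of Visits 2, 3 or 4".
- Inclusion criteria 9 and 10 require a positive bilateral reaction to challenge. Their details are redacted, and no nasal requirement is visible.

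**4. Which measures are exposed?** Split into single items, the seven secondary bullets give 10 items, of which 3 are nasal. Nasal ratings per subject: 3 items × 3 time points × 2 visits = 18. Primary itching ratings: 3 time points × 2 visits = 6, none of them nasal. These counts show which data are exposed, not how large any effect is.

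**5. Direction of effect, if the spray lowers nasal scores.**
- *Equal use.* Let a fraction p of each arm use the spray, let d be the true difference between arms without it, and let kd be the difference among users, with 0 ≤ k < 1 because the spray leaves less symptom for the drop to relieve. The observed difference is (1 − p)d + pkd = d[1 − p(1 − k)], which is closer to zero than d. If the spray took the same amount off every user's score whatever the arm, equal use would cancel and there would be no pull.
- *Unequal use.* Let the spray lower a user's score by s, with use p_B on bilastine and p_V on vehicle. The observed bilastine-minus-vehicle difference is d − s(p_B − p_V). If vehicle subjects use it more, the term −s(p_B − p_V) is positive and makes bilastine look less effective on the nasal items. Randomization does not remove this, because the use follows treatment.

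The documents give none of p, k or s, so no value is offered.

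**6. Avoidance period under the fix.** Summary of Visit Schedule: Visit 2 on Day −21 ± 3, Visit 5 on Day 8 ± 3, follow-up call on Day 15 ± 3.
- Start: −21 − 7 = Day −28.
- To Visit 5: 8 − (−28) = 36 days. With windows, shortest 5 − (−25) = 30 and longest 11 − (−31) = 42.
- To the call: 15 − (−28) = 43 days. With windows, 12 − (−25) = 37 to 18 − (−31) = 49.

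Each figure is one day less if there is no Day 0.

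**The case against.** The strongest reply is that only a synopsis is available. Synopses condense, and a full disallowed-medication section is where routes would be spelled out. The intent was probably to bar all antihistamines. A reader might infer that the trial permits the spray, but the documents do not support that: they show only that the synopsis does not forbid it. This limit stands, and the point is confined to the text supplied.

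The second reply is materiality. The documents name no product in the remaining class, give no usage rate and do not say that such a spray would change these scores. The risk-benefit summary reports nasal benefit for oral bilastine only, which is indirect at best. This stands too, so the effect is an assumption and its size is left open. Calling it small would be as unsupported as calling it large.

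The third reply is that the stated hypotheses concern ocular itching, and no visible hypothesis or multiplicity rule is attached to the nasal items. That is correct. A reader might infer that the primary result is at risk, but nothing in the documents shows that a nasal spray affects itching in the eye.

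Treatment-dependent use also has limited opportunity. The synopsis describes one dose about 16 hours before the Visit 4b challenge and one about 15 minutes before the Visit 5 challenge. Such use would have to arise in those 16 hours, or in the interval after Visit 4b in response to how that challenge went. This narrows the bias route without closing it.

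What remains is a stated rule which, followed exactly, admits a drug of the same class acting where a secondary measure is scored.

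**Conclusion.** The point holds in a limited form and is one to consider, with medium confidence. The synopsis wording leaves a plain intranasal H1 antihistamine outside exclusion criterion 6 while three nasal symptoms are secondary efficacy measures. The exposure is 18 nasal ratings per subject and none of the 6 primary ratings. Any distortion of the nasal comparisons rests on assumptions that the documents do not settle: that some subjects use such a spray, that it lowers nasal scores, and either that it leaves the drop less to relieve or that its use differs by arm. Its size cannot be estimated. The conclusion would lapse if a fuller medication section already names the intranasal route; only the synopsis wording would then need aligning.

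**What to change.** Reword the first item of the antihistamine line to *systemic, ocular or intranasal H1 antihistamine*. Keep the 7-day washout and the existing note that allows anti-allergy eye drops once a visit's evaluations are complete. Align any fuller concomitant-medication section with it. Do not deal with spray use by dropping subject-visits from the analysis after randomization, because use could depend on how well the assigned drop works.

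The cost is one route word and possibly a few more screen failures among spray users. They would have to stop from about Day −28 to Visit 5, or to about Day 15 if the study period is read as including the follow-up call; the sponsor should say which applies. Subjects already have to avoid systemic and ocular antihistamines and decongestants over the same period.
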